5.1.4 Medical History

Medical history events will be coded using MedDRA version 20.1. The medical history events, other than ITP, will be summarized by primary system organ class (SOC) and preferred term (PT) for each starting dose and overall.

Medical history data will be listed.

5.1.5 Prior and Concomitant Medications

All medications will be coded according to the WHODRUG dictionary WHO-DDE B2, September 2017.

The following medications will be summarized by Level 4 classification and preferred name for ITP and rescue medications, and by Levels 2 and 3 classifications for other medications for each starting dose and overall:

- Prior ITP medications
- Other prior medications

Concomitant and post-treatment medications will be summarized for each dose level and overall:

- Non-rescue ITP medications taken during the main on-treatment period
- Non-rescue ITP medications taken during the LTE on-treatment period
- ITP medications taken post treatment period
- Rescue medications taken during the main period
- Rescue medications taken during the LTE period
- Other concomitant and post-treatment medications taken during the main period
- Other concomitant and post-treatment medications taken during the LTE period

Medications will be attributed to the dose level where the medication is taken during the dose level. The same medication may be attributed to more than one dose level. Medications started after the date of last dose of study drug will be attributed to the last dose level received.

Separate listings will be provided for each category of medications.

5.2 Protocol Deviations

Protocol deviations will be identified and classified into minor vs. major by the Sponsor prior to database lock. The categories of protocol deviations are: Concomitant Medication, IP and Dosing, Enrollment Criteria, Informed Consent, Laboratory/Procedures Required, Safety and Visit Schedule.

Major protocol deviations will be tabulated by the deviation categories, starting dose and overall for patients who are in the ITT population.

A patient data listing with deviation category and deviation details will be provided for patients with major protocol deviations.

Patients impacted by Covid-19 will be summarized upon data availability, such as discontinuation due to Covid-19, protocol deviation due to Covid-19, and visit(s) impacted by Covid-19 as collected in eCRF, etc.

5.3 Study Drug Treatment Exposure and Compliance

Study drug treatment information will be summarized and documented in the Safety Population. Descriptive statistics will be done for all patients in the main treatment period and in the LTE treatment period in separate tables, as well as for main + LTE period. Patient data listings will be listed by starting dose, patient and study visit.

5.3.1 Actual Duration of Study Drug Exposure (days)

- Actual duration of study drug exposure in main treatment period (days) = (Date of last dose in main treatment period – Date of first dose in main treatment period) + 1, regardless of unplanned intermittent interruption
- Actual duration of study drug exposure in LTE treatment period (days) = (Date of last dose in LTE treatment period) + 1, regardless of unplanned intermittent interruption

In addition, duration of treatment exposure will also be summarized categorically by cycles.

5.3.2 Actual Total Cumulative Dose (mg)

Actual total cumulative dose in main treatment period (mg) = Sum of (Dose Level $_i$ (x2 if BID) x actual duration of study drug exposure in main treatment period for Dose Level $_i$ – total # of doses missed in Dose Level $_i$ during main treatment period))

Actual duration of study drug exposure in main treatment period for each dose level will be based on (Date of last dose in Dose Level $_i$ – Date of first dose in Dose Level $_i$) + 1, regardless of unplanned intermittent interruption

For patients who only had one dose level, the actual duration of Dose Level_i is the same as duration of study drug exposure in Section 5.3.1.

For patients with more than one dose levels:

- Date of first dose for the starting dose level is date of first dose taken at Cycle 1 Day 1.
- Date of first dose for the subsequence dose levels is the date of dosing reported on the Study Drug Administration eCRF where a dose adjustment was made. If the date of dosing is missing, then the date of visit where dose adjustment made will be used.
- Date of last dose for Dose Level_i is the date of first dose of the next dose level -1.
- Date of last dose for the last dose level is the date of last dose reported on the End of Study form.

Actual total cumulative dose in LTE treatment period (mg) = 400 mg x2 if BID x actual duration of study drug exposure in LTE treatment period – total # of doses missed in LTE treatment period)

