	CXD1 (first day of each cycle) Every 28 days for 6 months	Every 3 months	Last day of active rilzabrutinib (PRN1008) treatment	End of Study (4 week post last dose)	Early Withdrawal/ Unscheduled visit
Clinic visits ¹	X	Х	Х	Х	Х
AEs	X	Х	Х	Х	Х
Concomitant Medications	X	Х	Х	Х	Х
Weight	X	Х	Х	Х	Х
Physical Exam ⁷	X	Х	Х	Х	
Vital Signs	X	Х	Х	Х	Х
Urinalysis	X	Х	Х	Х	Х
Pregnancy test ²	X	Х	Х	Х	Х
Serum Chem	X	Х	Х	Х	Х
Hematology, differential, retics.	X	Х	Х	Х	Х
T/B/NK/monocyte counts ³	X	Х	Х	Х	
PT/INR PTT	X	Х	Х	Х	
ITP-BAT Bleeding Scale	X	X	X	X	Х

- 1. Clinic/laboratory visit windows are ± 7 days for all dosing period and lab visits.
- 2. Urine pregnancy test for women of childbearing potential only.
- 3. T/B/NK/monocyte counts (i.e., CD3, CD4, CD8, CD14, CD19, CD16/56), and B cell subsets (i.e., naïve, memory and plasmablasts), at D169, every 6 months during the active treatment period and at End of Study.
- 4. PT/INR, PTT: only if needed to follow up on bleeding adverse events.
- 6. At each dosing cycle, patient should take their dose in the morning before the clinic visit, and the PK sample is taken at random times after last dose (with time of last dose recorded on CRF, no time window).
- 7. Full physical exam at End of Study, abbreviated physical exam at all other visits.
- 8. After the initial 6 months of weekly LTE visits patients will visit monthly for an additional 6 months (total of 12 months of LTE) and then every three months until they are no longer on study.

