3.4 Analysis Timepoints and Definitions

3.4.1 Observation Period

The observation period will be divided into 3 segments:

- 1) The **pre-treatment period** is defined as the period to the date of first dose of study drug.
- 2) The **on-treatment period** is defined as the period from the first dose of study drug to the last dose of study drug + 1. The on-treatment period includes the main treatment period and the LTE period.
 - Main on-treatment period is defined as from the date of first dose of study drug
 - to the date of the last dose of study drug + 1, if the patient did not enter LTE.
 - to the date before the first dose of study drug during LTE, if the patient entered LTE.
 Date of first dose in LTE is based on the date of dosing reported on C1D1_LTE Study
 Drug Administration eCRF.
- 3) The **post-treatment period** is defined as the period from the end of the on-treatment period. That is, the 4-week post treatment follow up period per protocol.

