3.9 Data base lock

The database is planned to be locked approximately 4-6 weeks after all patients have completed or discontinued the main study period.

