5.3.3 Actual Average Daily Dose (mg/day)

Actual average daily in main treatment period (mg/day) = Actual total cumulative dose in main treatment period (mg)/ Actual duration of study drug exposure in main treatment period (days)

Actual average daily in LTE treatment period (mg/day) = Actual total cumulative dose in LTE treatment period (mg)/ Actual duration of study drug exposure in LTE treatment period (days)

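### SAP Part A 5.3.2 ends the main-period cumulative dose of multi-level patients at the End of Study form date with no cap, so extension doses can enter it, or it can be missing, for escalated patients who rolled directly into the LTE

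*SAP*

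**What the plan says.** SAP Part A 5.3.2 builds the main-period cumulative dose by summing, over dose levels, daily dose times days at that level, less missed doses. The end date of the last level depends on how many levels the patient had.

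- **One level:** "the actual duration of Dose Level_i is the same as duration of study drug exposure in Section 5.3.1". Section 5.3.1 stops at the "Date of last dose in main treatment period".
- **More than one level:** "Date of last dose for the last dose level is the date of last dose reported on the End of Study form". No exception is made for LTE entrants.

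Elsewhere the same SAP says:

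- Section 3.4.1 runs the main on-treatment period "to the date before the first dose of study drug during LTE, if the patient entered LTE", and takes that first LTE date from the C1D1_LTE dosing page.
- Table 5 (first six months of extension) treats Day 169 as the rollover visit and has no End of Study column. Table 6 (extension continued) has the column "End of Study (4 week post last dose").
- Section 5.3.3 defines average daily dose as "Actual total cumulative dose in main treatment period (mg)/ Actual duration of study drug exposure in main treatment period (days").
- Section 3.9 plans for the database to be "locked approximately 4-6 weeks after all patients have completed or discontinued the main study period", and Section 5.1.1 reports patients still ongoing in the LTE as a disposition category.

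**The concern.** One exposure table uses two end-date rules. A patient who started and stayed at 400 mg BID is cut off at the end of the main period. A patient who escalated to 400 mg BID is cut off at whatever last-dose date the End of Study form holds. For someone who rolled directly into the LTE, the schedules place the End of Study visit after the LTE, so the final 400 mg BID segment would run through the extension. Those days are also the whole content of the LTE cumulative dose, so the main and LTE figures would overlap.

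Section 5.3.3 then mixes the two spans, with an LTE-inclusive dose over a main-only duration. The result can exceed any dose the trial gives. For patients still in the LTE at lock there is no End of Study date at all. Part A states no fallback, and Section 3.5.2 does not impute other missing data. The Part B SAP (4.7.1), by contrast, does set a cut-off date for patients ongoing in the LTE.

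**Working it through.** The plan gives no cumulative-dose figure to reproduce, so the check applies its formula to its own dosing schedule.

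**Inputs**

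- Daily doses of 200, 400, 600 and 800 mg for 200 mg QD, 400 mg QD, 300 mg BID and 400 mg BID (SAP 2.2).
- 28 days per level before escalation (SAP 2.2, Tables 1 and 2).
- Escalated patients continue to 24 weeks (168 days) at 400 mg BID (Protocol 4.8). Three escalation cycles plus six make nine, within the ten that SAP 3.4.3 allows from protocol version 9.0.
- LTE dose 400 mg BID = 800 mg/day (SAP 5.3.2).
- Assumed: no missed doses; the form holds the last LTE dose; LTE length L of 28 to 336 days, because the documents give no individual lengths.

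**Step 1. Value intended by 3.4.1 and 5.3.1 (252-day course)**

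28×200 + 28×400 + 28×600 + 168×800 = 5,600 + 11,200 + 16,800 + 134,400 = 168,000 mg. Average: 168,000 / 252 = 667 mg/day.

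**Step 2. Value under the rule as written**

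Cumulative dose = 168,000 + 800×L. Average = that sum / 252.

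| LTE days | 'Main' dose (mg) | Average (mg/day) |
|---|---|---|
| 28 | 190,400 | 756 |
| 42 | 201,600 | 800 |
| 84 | 235,200 | 933 |
| 168 | 302,400 | 1,200 |
| 336 | 436,800 | 1,733 |

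The highest planned dose, 800 mg/day, is reached when 168,000 + 800×L = 800×252 = 201,600, so L = 33,600 / 800 = 42 days.

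**Step 3. Other dosing paths**

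- Cohort 1 with a 168-day main period (28 days at each of three levels, then 84 days at 400 mg BID): true 100,800 / 168 = 600 mg/day. As written: 123,200 / 168 = 733 at 28 LTE days, 235,200 / 168 = 1,400 at 168, and 369,600 / 168 = 2,200 at 336.
- Cohort 3 (28 days at 300 mg BID, then 168 days at 400 mg BID; 196 days): true 151,200 / 196 = 771 mg/day. As written: 173,600 / 196 = 886 at 28 LTE days, 285,600 / 196 = 1,457 at 168, and 420,000 / 196 = 2,143 at 336.

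**Step 4. Double counting**

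With 168 LTE days the main total is too high by 302,400 − 168,000 = 134,400 mg. The LTE cumulative dose for the same patient is 800×168 = 134,400 mg. The same doses sit in both.

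**Step 5. Compliance (5.3.4)**

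If the planned dose uses the true main period, the 168-day LTE case gives 302,400 / 168,000 = 180%, for which there is no category. If the planned dose uses the same overlong span, compliance is 100% with no missed doses and cannot exceed it. It would then cover main plus LTE days while subtracting only main-period missed doses.

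**The case against.** The strongest reply is that the End of Study form is a case report form page, not necessarily the End of Study visit in Table 6, and the eCRF is not among the documents. Section 5.1.1 needs separate reasons for leaving the main study and for leaving the LTE, and Section 3.4.11 uses a last-dose date in the main study. Some main-study completion record must therefore exist for patients still in the LTE. If that record is the form meant, the date is right and nothing is missing. This stands as a condition on the finding. It does not remove it, because the SAP names only one such form and the rollover schedule shows no End of Study visit.

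A second reply is that the quantity is labelled as main-period and Section 3.4.1 bounds that period, so a programmer would cap the date. The intent is indeed clear. But the explicit bullet says otherwise, and a programmer who caps the date departs from the text.

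Three stronger readings are tempting and not supported:

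- *Every escalated LTE entrant is affected.* Patients who completed before protocol version 9.0 and entered the LTE later (SAP 2.2) had an End of Study visit before the LTE, so their date may be correct. Patients ongoing at lock would have a missing value, not an inflated one.
- *The exposure data behind the Part A safety conclusions are wrong.* Exposure duration (5.3.1) uses the main-period last dose. Adverse event rates use patient-years in the observation period, and events are attributed by dose-level start dates (5.5.1). No efficacy endpoint uses this date.
- *Compliance must exceed 100%.* That follows only under one reading of the planned-dose denominator, which 5.3.4 leaves open.

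**Conclusion.** The bullet is wrong as written. It has no cap at the end of the main period and conflicts with Sections 3.4.1 and 5.3.1 and with the rule for one-level patients.

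The consequence is conditional. It applies to escalated patients who rolled directly into the LTE, and only if the form records the last LTE dose, as Table 6 implies. In that case each LTE day adds 800 mg to the main-period total, and patients still in the LTE at lock have no value. In the 252-day example the average daily dose passes the highest planned dose only after 42 LTE days; shorter extensions give a wrong but plausible-looking figure. The documents give neither the LTE lengths nor the number of patients in each group, so the effect on the summary tables cannot be sized.

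The damage is confined to descriptive cumulative dose and average daily dose, and to compliance depending on its denominator. It is worth correcting because the remedy is simple and uses dates the SAP already defines.

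**What to change.** Replace the bullet in 5.3.2 with a rule that the last dose level ends at the last main-period dose, as in Sections 3.4.1 and 5.3.1. For patients who rolled directly into the LTE, that is the day before the first dose on the C1D1_LTE page. Use the End of Study form date only for patients who did not enter the LTE. Patients who completed before version 9.0 and entered the LTE later take their last main-period dose, so that the gap off drug is not counted.

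The text change is small and needs no new data, only a programming change. The Part B SAP (1.1) says that a Part A study report has already been prepared, so the real cost is checking the reported cumulative dose, average daily dose and compliance tables against this rule, and re-running them if the uncapped date was used.

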5.3.4 Study Drug Compliance (%)

Compliance with study drug will be calculated as the actual total cumulative dose (mg) taken divided by the planned number of doses (mg), i.e., do not adjust for missed doses, expressed as a percentage.

Compliance will be summarized by descriptive statistics for the main treatment period and LTE treatment period. The number and percentage of patients with 100% compliance, greater than 80% but less than 100% compliance and less than 80% compliance will be tabulated.

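### Read literally, the Part A cumulative-dose formula subtracts a count of missed doses from milligrams, and its unmatched bracket leaves the intended exposure and compliance derivation unstated

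*SAP*

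**What the plan says.** The Part A SAP builds its exposure measures in four steps.

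- **Duration (5.3.1).** For the main period this is last dose date minus first dose date, plus 1. The LTE line has only the end date: "Date of last dose in LTE treatment period) + 1, regardless of unplanned intermittent interruption".
- **Cumulative dose (5.3.2).** The main-period formula opens "Actual total cumulative dose in main treatment period (mg) = Sum of (Dose Level", multiplies by 2 for BID and by the days at that level, then subtracts the number of doses missed at that level "during main treatment period". It closes two brackets where only one is still open. The LTE formula is "400 mg x2 if BID x actual duration of study drug exposure in LTE treatment period", less the "total # of doses missed in LTE treatment period", followed by a closing bracket with no opening one.
- **Average daily dose (5.3.3).** "Actual total cumulative dose in main treatment period (mg)/ Actual duration of study drug exposure in main treatment period (days"), and the same form for the LTE.
- **Compliance (5.3.4).** The numerator is the cumulative dose, "divided by the planned number of doses (mg), i.e., do not adjust for missed doses, expressed as a percentage". Patients are then tabulated at 100%, between 80% and 100%, and below 80%.

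**The concern.** The first term of each cumulative-dose formula is in milligrams and the subtracted term is a count of doses. By ordinary order of operations, one missed 400 mg dose lowers the total by 1 mg. Average daily dose and compliance are both computed from that total, so they inherit the fault.

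The stray bracket shows that something is missing, but its place is not stated, and the place decides the answer. The SAP gives no worked example for this derivation. Section 4.7.1 of the Part B SAP cannot settle it, because it defines compliance by compliant days, not by milligrams.

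At stake is whether the Part A exposure tables describe what patients took. In a dose-finding study, a reader uses such tables to judge whether poor response at a dose level might reflect poor adherence.

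**Working it through.** The SAP states no numerical result for these quantities, so there is no figure to reproduce. The check evaluates the formula under each reading.

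**Inputs.** Dose levels are 200 mg QD, 400 mg QD, 300 mg BID and 400 mg BID (Part A SAP 2.2). Treatment lasts 24 weeks = 168 days (protocol 4.8). The missed-dose counts are illustrative. Let D = mg per dose, f = doses per day, T = days and m = missed doses. The planned dose is taken as D × f × T, which at 400 mg BID is 400 × 2 × 168 = 134,400 mg over 336 doses.

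**Readings.**
- A, literal, stray bracket ignored: D × f × T − m
- B, bracket before the frequency: D × (f × T − m)
- C, bracket before the duration: D × f × (T − m)

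**400 mg BID, 50 of 336 doses missed.**
- A: 134,400 − 50 = 134,350 mg; /134,400 = 99.96%; /168 = 799.7 mg/day
- B: 400 × (336 − 50) = 114,400 mg; 85.1%; 681.0 mg/day
- C: 800 × (168 − 50) = 94,400 mg; 70.2%; 561.9 mg/day

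Reading B agrees with a direct count: 286/336 = 85.1% of doses taken. Reading C moves this patient into the below-80% row.

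**Missed doses needed to fall below 80%.**
- A: more than 0.20 × 134,400 = 26,880, when only 336 are scheduled
- B: more than 0.20 × 336 = 67.2, so 68; at 68, 107,200/134,400 = 79.76%
- C: more than 0.20 × 168 = 33.6, so 34, which is 34/336 = 10.1% of doses

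**Lowest value under A.** With every dose missed, m = f × T and compliance is 1 − 1/D: 99.50% at 200 mg, 99.67% at 300 mg and 99.75% at 400 mg. For a full Cohort 1 escalation (28 days each at 200 mg QD, 400 mg QD and 300 mg BID, then 84 days at 400 mg BID), the planned dose is 5,600 + 11,200 + 16,800 + 67,200 = 100,800 mg over 280 doses, so the floor is (100,800 − 280)/100,800 = 99.72%.

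**Behaviour of C.** At QD, f = 1 and C equals B, so the error affects only the BID levels. At BID, more than 168 missed doses gives a negative cumulative dose.

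**LTE.** The printed duration is a date plus 1, not a number of days, so no LTE dose can be computed from the text as it stands.

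**The case against.** The strongest reply is that the line is malformed, so it has no true literal reading. Both formulas have one closing bracket too many, and the opening one may have been lost when the PDF was read. Signs are missing or garbled elsewhere in the same text, for example in the study-day formula (Part A SAP 3.4.10) and the LTE rescue window (Part B SAP 4.4.2). Only reading B subtracts doses from doses, and C can go negative. Section 5.3.4 fits B too: its denominator is in mg and unadjusted for missed doses, and a below-80% row is planned.

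Much of this stands. B is very probably what was meant, and the fault may be one of notation. What remains is that no legible sentence states B, and C needs only a different place for the same bracket.

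Two stronger inferences are tempting, and the documents support neither:

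- **That the reported compliance and average daily dose are wrong.** That would require the program to have followed A or C, and nothing shows this.
- **That no patient could ever appear below 80%.** This holds under A only if the planned dose is dose × frequency × actual duration. Section 5.3.4 suggests that denominator but does not spell it out. If it meant the full 168 days, a patient stopping at day 84 with nothing missed would score 800 × 84 / 134,400 = 50% even under A.

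The reach is also limited. These are descriptive Safety-population summaries (5.3). Efficacy uses the ITT population and counts everyone who received a dose level at least once (5.4). The 75% compliance rule for sentinel cohorts served the safety monitor's review during the study, not these tables.

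**Conclusion.** The point holds conditionally. The cumulative-dose formulas for both periods, as they stand, do not define the quantity they name. Literal programming would make missed doses almost invisible (99.96% against 85.1% in the example). A misplaced bracket would count each missed BID dose twice (70.2%). The LTE duration is separately incomplete.

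The sizes rest on 400 mg BID for 168 days, 50 missed doses, and a planned dose based on actual duration. The consequence is confined to the cumulative dose, average daily dose and compliance tables; no efficacy result described in the legible text depends on them. It should be corrected, but it does not threaten the trial's main conclusions.

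**What to change.** In the Part A SAP, state:

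- Cumulative dose = sum over dose levels i of Dose_i × (k_i × days_i − missed doses_i), with k = 1 for QD and 2 for BID, and the same form for the LTE.
- Compliance denominator = sum over i of Dose_i × k_i × days_i.
- LTE duration = last LTE dose date − first LTE dose date + 1.

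Section 1.1 of the Part B SAP says that the Part A main period is complete and its study report prepared. For that period the practical step is therefore to confirm that the programmed derivation matches these definitions, and to correct any table that does not.

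The cost is a wording change and a program check, with a rerun of the exposure tables only if the check fails. No new data are needed.
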